8.2.4 Clinical Safety Laboratory Assessments

Blood and urine samples for determination of clinical chemistry, haematology, coagulation, urinalysis, viral serology, pregnancy, and other laboratory tests will be taken at the visits indicated in the SoA of the relevant individual module. Collection times begin from the start of the infusion.

The date and time of each collection will be recorded in the appropriate eCRF. Following SRC review of emerging data, the timing of laboratory safety assessment samples may be adjusted for subsequent cohorts. Additional sampling times may be added or removed if indicated by the emerging data.

Additional safety samples may be collected if clinically indicated at the discretion of the Investigator. The date, time of collection, and results (values, units, and reference ranges) will be recorded on the appropriate eCRF. Laboratory values will be repeated, confirmed, and followed up as appropriate.

Situations in which laboratory safety results should be reported as AEs are described in Section [8.3.5](#).

All laboratory safety analyses, including clinical chemistry, haematology, and urinalysis, will be performed at a local laboratory at or near to the Investigator site. Sample tubes and sample sizes may vary depending on laboratory method used and routine practice at the site.

Pregnancy tests may be performed at the site using a licensed test (urine or serum pregnancy test). Abnormal clinically significant laboratory results should be repeated as soon as possible (preferably within 24 to 48 hours).

The laboratory safety variables listed in [Table 12](#) will be measured.

Table 12 Laboratory Safety Variables

Haematology/Haemostasis (whole blood)		Clinical Chemistry (serum or plasma)	
Haemoglobin (Hb)		Creatinine	Chloride
Leukocyte count (WBC count)		Bilirubin, total	Cortisol ^a
Leukocyte differential count		Alkaline phosphatase	TSH ^a
Neutrophils		AST	Bicarbonate
Lymphocytes		ALT	BUN/urea nitrogen
Eosinophils		Amylase ^b	Lipase ^b
Platelet count		Albumin	LDH
Urinalysis		Potassium	Phosphate
Hb/erythrocytes/blood		Calcium, total	Uric acid
pH	Ketones	Sodium	Troponin I ^a
Protein/albumin	Bilirubin	BNP (or NTproBNP) ^a	
Glucose		Magnesium	Glucose
Microscopy (red and white blood cells, bacteria, casts, and crystals) only if urinalysis is abnormal		Total protein	ACTH ^a
Coagulation		Cholesterol	GGT
International normalised ratio (INR)		Triglycerides	Ferritin
Activated partial thromboplastin time (aPPT)		High-density lipoprotein (HDL)	Creatine kinase (CK)
Prothrombin time (PT)		Low-density lipoprotein (LDL)	
Fibrinogen		Pregnancy test (females of childbearing potential only)	
Viral Serology		Urine human chorionic gonadotropin (hCG)	Serum beta hCG
Hepatitis B and C	CMV	Others	
SARS-CoV-2		Serum immunoglobulins ^a	Beta-2 microglobulin ^a

^a At screening, at target dose (predose timepoint) and then as clinically indicated and at end of treatment visit.

^b Collected at screening, pre-infusion on each dosing day, and end of treatment visit.

Lipids: triglycerides, high density lipoprotein, low density lipoprotein, and cholesterol.

ACTH = adrenocorticotrophic hormone; ALT = alanine aminotransferase; AST = aspartate aminotransferase; BUN = blood urea nitrogen; CMV = cytomegalovirus; GGT = gamma-glutamyltransferase; LDH = lactate dehydrogenase; SARS-CoV-2 = severe acute respiratory syndrome coronavirus 2; TSH = thyroid-stimulating hormone; WBC = white blood cell.

NB. In case a patient shows an AST or ALT $\geq 3 \times$ ULN together with total bilirubin $\geq 2 \times$ ULN, refer to [Appendix E](#) for further instructions.

8.2.4.1 Troponin I and Brain Natriuretic Peptide

Blood samples for troponin I and BNP or NTproBNP measurements will be collected, as specified in the SoA within the relevant module and below:

- Screening
- Target dose pre-infusion (C1D8 – pre-infusion)
- As clinically indicated
- EoT visit

Troponin T may be collected using a standard assay instead of troponin I, provided the results remain within normal range. However, if an abnormal troponin T value is recorded, collection of troponin I will be required thereafter, as it is more cardiac-specific. Dosing with AZD0466 must not occur until results are obtained and are normal. If an unscheduled ECG is performed, an electrolyte panel (ie, calcium, magnesium, potassium, and troponin I) must be done to coincide with the ECG assessment, including referral to a cardiac specialist. Isolated troponin elevations are not sufficient to trigger dosing changes and should be evaluated in the context of other cardiac findings.

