6.4 Study Intervention Compliance

When patients are dosed at the site, they will receive study intervention directly from the Investigator or designee, under medical supervision. The date, and time, of dose administered in the clinic will be recorded in the source documents and recorded in the eCRF. The dose of study intervention and study patient identification will be confirmed at the time of dosing by a member of the study site staff other than the person administering the study intervention.

Any changes from the dosing schedule, dose reductions and dose discontinuations should be recorded in the eCRF. The reason should also be documented.

Use of doses in excess of that specified in the protocol is considered to be an overdose. Overdose procedures to be followed in the event of overdose are described in Section [8.4](#).

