6.6.6.1 Dose Modifications

AZD0466 may be withheld and the dose reduced due to haematologic or non-haematologic toxicities. In general, no AZD0466 dose modification is required if a patient experiences a Grade 1 or Grade 2 AEs. However, AZD0466 treatment should be modified or discontinued when the AEs described in this section are observed.

AZD0466 dose modification is at the discretion of the Investigator. However, some considerations have been provided.

- For platelet and liver changes, consider Q2W ([Table 6](#)) and at second occurrence, consider triggering dose reductions ([Table 7](#)).
- For AEs other than platelet and liver-related toxicities, consider reducing the dose ([Table 7](#)).
- Dose modifications can be done in two ways, which include dose reduction and frequency change (from weekly to bi-weekly schedule). Frequency changes are not possible during ramp-up. A maximum of 3 dose modifications is acceptable, except for CTCAE Grade 3 or 4 haemorrhage and any intracranial haemorrhage or haematoma, of which only one event is allowed. See [Table 8](#), [Table 9](#), [Table 10](#), and [Table 11](#).

Table 6

Dose Frequency Changes

CCI

[figure not shown]
[figure not shown]

Table 7

Dose Reduction Modifications

CCI

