6.6.6.5 Cardiac Findings

AZD0466 should be withheld if any of the following occur at any time during study intervention:

- Symptomatic tachycardia
- Symptomatic hypotension
- QTcF shortening by 60 milliseconds compared to baseline, or interval value < 340 milliseconds, confirmed on at least 2 separate ECGs recorded 5 minutes apart
- QTcF prolongation of > 500 milliseconds or QTcF prolongation from baseline by 60 milliseconds, confirmed on at least 2 separate ECGs recorded 5 minutes apart
- Any other cardiac findings of CTCAE Grade ≥ 2 or considered by the Investigator to be clinically significant.
- AZD0466 should be permanently discontinued if a CTCAE Grade ≥ 3 cardiac AE of any duration occurs during study intervention, if considered by the Investigator to be related to study intervention.

Further investigation of the cardiac findings should be considered, including referral to a cardiac specialist. Patients should be monitored closely. AZD0466 may be restarted after resolution of cardiac findings to the patient's baseline at the discretion of the Investigator and after discussion with the Study Physician.

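### Protocol 8.2.4.1 makes a normal result a condition of dosing, yet says an isolated troponin elevation is not enough to change dosing; nothing says which sentence governs

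*Protocol*

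**What the plan says.** Protocol Section 8.2.4.1 schedules troponin I and BNP (or NTproBNP) at screening, before the Cycle 1 Day 8 infusion, when clinically indicated, and at end of treatment. Troponin T may be used instead while it stays normal, but "if an abnormal troponin T value is recorded, collection of troponin I will be required thereafter, as it is more cardiac-specific".

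The next sentence reads "Dosing with AZD0466 must not occur until results are obtained and are normal". It carries no exception. After one further sentence, on unscheduled ECGs, the paragraph closes with "Isolated troponin elevations are not sufficient to trigger dosing changes and should be evaluated in the context of other cardiac findings".

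Section 6.6.6.5 opens its list of cardiac reasons for holding treatment with "AZD0466 should be withheld if any of the following occur at any time during study intervention". The list covers symptomatic tachycardia, symptomatic hypotension, QTcF shortening or prolongation, and a general entry for other cardiac findings that are Grade 2 or higher or that the Investigator judges clinically significant. Troponin is not named.

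**The concern.** One paragraph gives a site two answers on whether to infuse. The first sentence makes an abnormal result, by itself, a reason not to dose. The last says that an isolated elevation, by itself, is not a sufficient reason to change dosing.

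The protocol's risk table (Section 2.3.1, Table 1) lists cardiovascular toxicity as an important potential risk, and Cycle 1 Day 8 is both the first target dose and inside the 28-day DLT period. Section 8 does not allow waivers. A site that infuses on the strength of the last sentence therefore breaks an absolute prohibition, while a site that follows the prohibition withholds a planned dose for a reason the paragraph calls insufficient. SAP Section 4.3.7 has a deviation category for departures from the prescribed dosing regimen, but the documents do not settle which of these two actions would be the departure.

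**Working it through.** The plan gives no figure to reproduce. The check is a comparison of texts, followed by a count of doses.

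**Test case.** Troponin I is raised before the Cycle 1 Day 8 infusion, with no other cardiac finding.

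| Source | Applied to the test case |
|---|---|
| 8.2.4.1, prohibition | No infusion while the result is abnormal |
| 8.2.4.1, closing sentence | The elevation alone is not enough to change dosing |
| 6.6.6.5 | Troponin not named; the general entry turns on grade or Investigator judgement |
| 6.6.6.5, restart | After return to the patient's own baseline, with Study Physician discussion; 8.2.4.1 requires a normal value instead |
| Tables 13 and 14, troponin footnotes | Cover only the switch from troponin T to troponin I |
| SAP | No rule on troponin and dosing |

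The first two rows conflict and no other row decides between them.

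**Where it can arise.**
- Cycle 1 Day 8 is the only scheduled on-treatment sample taken before a dose. From Cycle 2 the only scheduled sample is at end of treatment (Table 14).
- Screening is exposed as well. The cardiac eligibility criteria (Section 5.1 criterion 9, Section 5.2 criterion 11) do not name troponin, so a patient could meet them with a raised value and still be barred from the first dose by the prohibition.
- Clinically indicated samples can raise the same question at any time.

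**Effect on Cycle 1 target doses.** Inputs: target doses on Days 8, 15 and 22 (Section 10.6.6.1); visit window of ±2 days (Table 13); abnormal clinically significant results repeated preferably within 24 to 48 hours (Section 8.2.4); doses at least 72 hours apart (Section 6.2.1); at least 2 target doses in Cycle 1 for the response-evaluable set and, absent a DLT, for the DLT-evaluable set (Table 26, Section 10.6.6.5).

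- *Normal repeat by Day 10.* Day 8 + 2 = Day 10, inside the window. The gap to Day 15 is (15 − 10) × 24 = 120 hours, above 72. Doses given: 3 of 3.
- *Day 8 dose missed, Days 15 and 22 given.* Doses given: 2 of 3 = 67%, which meets the minimum.
- *Day 8 and one further target dose missed.* Doses given: 1 of 3 = 33%. The patient leaves the response-evaluable set, and leaves the DLT-evaluable set unless a DLT has occurred.

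Only the third case changes an analysis set.

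**The case against.** The strongest reply is that the sentences can be read together. Section 6.6.6.1 says "Dose modifications can be done in two ways, which include dose reduction and frequency change". If the closing sentence of 8.2.4.1 is about modifications in that sense, the prohibition is just a pre-dose check: the infusion waits for a normal value, and the dose and frequency stay as they were. Several rows of the toxicity tables work this way, holding treatment and then restarting at the same dose.

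This reading is possible but the text does not secure it. Section 8.2.4.1 does not use the term dose modification, and the term it does use is undefined. Section 6.4 counts schedule departures as changes: "Any changes from the dosing schedule, dose reductions and dose discontinuations should be recorded in the eCRF". The reading also fails for a value that stays raised, because the hold then has no end although the elevation alone was said to be insufficient. Confining the prohibition to the troponin I that follows an abnormal troponin T does not help either, since an isolated troponin I elevation still meets both sentences.

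The reply also points to routes for advice. Section 6.6.7 sends undescribed scenarios to the Study Physician, and Section 8 sends immediate safety concerns to the Sponsor. These lessen the practical risk, but they do not say which sentence governs.

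One part of the reply stands in full. A reader might infer that a hold on Day 8 leaves at most two of the three target doses. The visit window and the repeat test show that all three can be kept.

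**Conclusion.** The conflict is real and unresolved, and it is one of wording. The prohibition makes an abnormal value sufficient to stop an infusion; the closing sentence says an isolated elevation is not sufficient to change dosing. For the test case a site has no documented way to choose.

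Two stronger conclusions are not supported. A reader might take the closing sentence to forbid any change of dosing for an isolated elevation. It says only that the elevation does not suffice and must be weighed with other findings. A reader might also expect a material loss of evaluable patients. That needs a second missed target dose. In addition, a patient with a DLT remains DLT-evaluable, and DLT-non-evaluable patients are replaced (Section 10.6.6.3).

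The main consequence is inconsistent handling between sites of a signal for a named cardiac risk, with unclear deviation reporting as a by-product. The size cannot be given, because the documents contain no rate of isolated troponin elevation. The conclusion assumes that the prohibition covers the scheduled pre-dose troponin results, which is its plain sense in that section.

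**What to change.** The sponsor should replace the two sentences in Section 8.2.4.1 with one instruction for isolated troponin elevations. It should state which results and which sampling times it covers, and whether holding an infusion counts as a change of dosing. Section 6.6.6.5 should then be brought into line, both on whether troponin belongs among its cardiac findings and on the restart standard, which is baseline there and normal in 8.2.4.1. The clinical content is for the sponsor to decide; this review takes no position on it.

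The cost is a short wording amendment to two protocol sections. No sample size, endpoint or analysis changes. SAP Section 4.3.7 needs no new category, because once the instruction is single the existing dosing-regimen category can be applied consistently.

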8.2.5 Other Safety Assessments

8.2.5.1 Cardiac MUGA/MRI/ECHO

A cardiac MUGA/MRI/ECHO to assess LVEF will be conducted. The modality of the cardiac function assessments must be consistent within a patient ie, if ECHO is used for the screening assessment then ECHO should also be conducted at subsequent assessments. A 28-day follow-up assessment will be required if an on treatment assessment was abnormal at the time of discontinuation of study intervention, to confirm reversibility of the abnormality. The patients should also be examined using the same machine and operator whenever possible.

Unscheduled assessments should be performed as clinically indicated, including after a clinically significant ECG finding (T wave inversion/flattening, significant QRS amplitude changes or symptomatic patient, etc). In case of any T wave abnormality, the ECHO, MRI, or MUGA should be repeated at the EoT visit to address the question of recovery during the off-treatment period.

Cardiac MUGA/MRI/ECHO should be performed as specified in the SoA.

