4.3.3 General Study Level Definitions

Baseline is the last non-missing value obtained prior to the first dose/administration of any study treatment and any information collected after first dose/administration of study treatment is regarded as post-baseline information. If two visits are equally eligible to assess patient status at baseline (e.g., screening and baseline assessments both on the same date prior to first dose/administration with no washout or other treatment in the screening period), the average is taken as the baseline value. For non-numeric laboratory tests (i.e. some of the urinalysis parameters) where taking an average is not possible then the best value is taken as baseline as this is the most conservative. In the scenario where there are two assessments on Day 1 prior to first dose, one with time recorded and the other without time recorded, the one with time recorded is selected as baseline. Where safety data are summarised over time, study day is calculated in relation to date of first treatment. For assessments on the day of first dose where time is not captured, a nominal pre-dose indicator, if available, serves as sufficient evidence that the assessment occurred prior to first dose. Assessments on the day of the first dose where neither time nor a nominal pre-dose indicator are captured is considered prior to the first dose if such procedures are required by the protocol to be conducted before the first dose. If no value exists before the first dose/administration, then the baseline value is treated as missing.

Change from baseline will be calculated as the post-dose value minus the baseline value as:

$$\text{post-baseline value} - \text{baseline value}$$

Percent change from baseline will be calculated as:

$$\frac{\text{post-baseline value} - \text{baseline value}}{\text{baseline value}} \times 100$$

Study day 1 is defined as the date of first dose of study treatment (Cycle 1 Day 1). For visits (or events) prior to first dose, study day is defined as (date of visit [event] – date of first dose of study treatment). For visits (or events) that occur on or after first dose of study treatment, study day is defined as (date of visit [event] – date of first dose of study treatment + 1).

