4.3.7 Handling of Protocol Deviations in Study Analysis

Important protocol deviations are defined as those deviations from the protocol likely to have an impact on the perceived efficacy and/or safety of study treatment.

The following general deviation categories will be defined. These deviations will be reviewed and assessed on a case-by-case basis by AstraZeneca to determine importance. Deviations considered to be important will be listed and discussed in the clinical study report (CSR) as appropriate. All decisions on importance will be made ahead of database lock and will be documented prior to the analysis being performed.

- Patients who deviate from entry criteria per CSP (Deviation 1)
- No baseline Lugano assessments on or before the date of first dose (Deviation 2)
- Received prohibited concomitant medications or therapies (Deviation 3)
- Patients deviating from prescribed dosing regimen (Deviation 4)
- Missed visits, assessments, or treatments that, in the opinion of the investigator, were due to Corona virus disease 2019 (COVID-19) global pandemic, and where there was a significant effect on either completeness, accuracy and/or reliability of the patient's data, or the patient's rights, safety or wellbeing (Deviation 5)
- Deviation from Good Clinical Practice as determined by medical review (Deviation 6)

None of the deviations should lead to subjects being excluded from any analysis populations described in the SAP, unless otherwise specified. However, if a deviation is serious enough to have a potential impact on the primary analysis, sensitivity analyses may be performed. The need for such a sensitivity analysis will be determined following review

of the protocol deviations ahead of database lock and will be documented prior to the analysis being conducted.

A list of all protocol deviations will be reviewed and decisions regarding how to handle these deviations in the analyses will be documented by the study team physician, clinical pharmacology scientist and statistician prior to database lock.

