5.6.10 Echocardiogram (ECHO)

5.6.10.1 Definitions and Derivations

In addition to screening, an ECHO should be done within 14 days after an abnormal ECG finding (T wave inversion/flattening, significant QRS amplitude changes or symptomatic patient, etc) or as soon as possible when clinically indicated. If an ECHO cannot be taken, a multi-gated acquisition (MUGA) scan to assess left ventricular ejection fraction (LVEF)

will be done. In case of any T wave abnormality, the ECHO (or MUGA) should be repeated at the 30-day follow-up visit to address the question of recovery, during the off-treatment period.

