5.6.10.2 Presentations

Absolute value, change from baseline and percentage change from baseline will be presented for LVEF.

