Table 8 Schedule of Activities for Module 1 Part A and Part B: Cycle 2 and Beyond and Follow-up

| Procedures | Cycle 2 (28 days) | | Cycle 3 and beyond (28 days) | | EoT | Follow-up | | Details in CSP section or appendix |
|--------------------------|-------------------------|---------|----------------------------------|----------------------------|-----|---|-----------------------------------|------------------------------------|
| Day | 1 | 8/15/22 | 1 | 8/15/22 | | Post-treatment FU visit (28 days after last dose) | Q3M after post-treatment FU visit | |
| Visit window | ± 2 days | | | | | ± 7 days | | |
| Physical examination | X | X | X | X | X | | | 8.2.1 |
| Weight | X | D15 | X | D15 | X | | | 8.2.1 |
| Vital signs | X | X | X | X | X | | | 8.2.2 |
| ECOG performance status | X | | X | | X | | | 8.2.5.2 |
| Concomitant medication | X | X | X | X | X | X | | 6.5 |
| Adverse events | X | X | X | X | X | X | | 8.3 |
| Safety ECGs (triplicate) | X | D8 | Even cycles only beginning at C4 | | X | | | 8.2.3, 10.8.2.3 |
| Cardiac MUGA/MRI/ECHO | | D8 | | D8, every 3 cycles from C5 | X | | | 8.2.5.1 |
| Fresh tumour sample | As clinically indicated | | | | | | | 10.8.6.3 |
| Survival status | | | | | | X | X | NA |
| Laboratory test | | | | | | | | |
| SARS-CoV-2 test | X | | X | | | | | 8.2.4 |
| Pregnancy test (WOCBP) | X | | X | | X | | | 8.2.4 |
| Haematology | X | X | X | X | X | | | 8.2.4 |
| Clinical chemistry | X | X | X | X | X | | | 8.2.4 |
| Serum immunoglobulins | | | | | X | | | 8.2.4 |
| Beta-2 microglobulin | | | | | X | | | 8.2.4 |
| Amylase and lipase | X | X | X | X | X | | | 8.2.4 |

| | | | | | | | | |
|--|---|---|---|---|---|--|--|-------------|
| Coagulation | X | X | X | X | X | | | 8.2.4 |
| Cortisol, ACTH, TSH | | | | | X | | | 8.2.4 |
| Troponin I ^a | | | | | X | | | 8.2.4 |
| BNP (or NTproBNP) | | | | | X | | | 8.2.4 |
| Urinalysis | X | X | X | X | X | | | 8.2.4 |
| Disease assessments | | | | | | | | |
| CT scan | Weeks 8, 16, 24, 36, 48 and thereafter every 24 weeks for R/R FL and MZL, and every 16 weeks for R/R MCL and R/R DLBCL, until disease progression | | | | | | | 8.1.2 |
| FDG-PET scan | Week 8, 24 and 48 and thereafter once a year. If confirmed CR, no further PET scans are required. | | | | | | | 8.1.2 |
| Bone marrow biopsy/aspirate | To confirm CR (if prior bone marrow involvement) or as clinically indicated | | | | | | | 8.1.1 |

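### The SAP summarises LVEF change from baseline with no condition on imaging modality, although the protocol requires one modality per patient and the SAP itself provides for a MUGA in place of an ECHO

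*Protocol*

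**What the plan says.** **Protocol 8.2.5.1** allows MUGA, MRI or ECHO for LVEF but fixes the choice within a patient: "The modality of the cardiac function assessments must be consistent within a patient". Its example is that "if ECHO is used for the screening assessment then ECHO should also be conducted at subsequent assessments". It gives no fallback to another modality, and it also asks for the same machine and operator where possible.

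**SAP 5.6.10.1** describes the post-screening scan differently: "In addition to screening, an ECHO should be done within 14 days after an abnormal ECG finding". The next sentence begins "If an ECHO cannot be taken, a multi-gated acquisition (MUGA) scan to assess left ventricular ejection fraction (LVEF" and goes on to say that such a scan will be done. Nothing there refers to the modality used at screening.

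**SAP 5.6.10.2** is one sentence: "Absolute value, change from baseline and percentage change from baseline will be presented for LVEF".

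**SAP 4.3.3** sets the general baseline rule: "Baseline is the last non-missing value obtained prior to the first dose/administration of any study treatment".

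**SAP Table 8**, like protocol Table 14, has a row for all three modalities with scans on Cycle 2 Day 8, then "D8, every 3 cycles from C5", and at end of treatment.

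**The concern.** A change from baseline measures a change in the patient only if both values come from the same method. The protocol evidently treats method variation as something to control. The SAP provides for a substitution that can break the pairing, and then gives no rule for the broken pair.

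The substitution sentence comes straight after the ECG-triggered scan. A switch made under it would therefore fall on a patient already under cardiac suspicion, where a clean comparison is most useful. Protocol Table 1 lists cardiovascular toxicity as an important potential risk, and LVEF is the only cardiac imaging result that the SAP plans to summarise. SAP 5.6 presents safety results by dose level or cohort, so one patient can carry visible weight in a small group. What is at stake is how a descriptive safety table reads, not an efficacy result.

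**Working it through.** There is no planned figure to reproduce. The check is a comparison of rules, followed by an illustration of size.

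**Step 1. Does any SAP rule remove or separate an off-modality value?**

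| SAP rule | Modality condition? |
|---|---|
| 4.3.3, baseline is the last non-missing pre-dose value | None |
| 4.3.4, the value nearest the scheduled date represents the window | None; an off-modality scan can be chosen over a same-modality scan in the same window |
| 4.3.7, named deviation categories | A modality switch is not named |
| 5.6.10.1, MUGA if an ECHO cannot be taken | None |
| 5.6.10.2, change and percentage change | None; no split or flag |

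Read literally, a later MUGA would be subtracted from a baseline ECHO and summarised with the same-modality pairs.

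**Step 2. What would that do to the numbers?** All inputs here are assumptions: a between-modality offset of 3, 5 or 10 LVEF points, a baseline of 60 or 52, and groups of 3 or 9.

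- Observed change = true change + offset.
- Spurious percentage change when true change is zero = 100 × offset / baseline.
- Shift in the group mean change from one switched patient = offset / n.

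| Offset | % change, baseline 60 | % change, baseline 52 | Mean shift, n = 3 | Mean shift, n = 9 |
|---|---|---|---|---|
| 3 | 100 × 3/60 = 5.0 | 100 × 3/52 = 5.8 | 3/3 = 1.0 | 3/9 = 0.33 |
| 5 | 100 × 5/60 = 8.3 | 100 × 5/52 = 9.6 | 5/3 = 1.67 | 5/9 = 0.56 |
| 10 | 100 × 10/60 = 16.7 | 100 × 10/52 = 19.2 | 10/3 = 3.33 | 10/9 = 1.11 |

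The sign can be either. With an assumed true fall of 10 points and an offset the other way, the observed change is −10 + 3 = −7, −10 + 5 = −5, or −10 + 10 = 0.

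**Step 3. Is SAP 5.6.10.1 otherwise in line with the schedule?** Not fully. Its text names ECHO and MUGA but not MRI. It mentions screening and triggered scans but not the scheduled on-treatment scans in Table 8. It puts the repeat scan after a T wave abnormality at a 30-day follow-up visit, where protocol 8.2.5.1 puts it at the end-of-treatment visit. These passages must be reconciled.

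**The case against.** **The protocol governs the sites.** A reader might infer that the SAP permits investigators to change modality. It does not: conduct follows the protocol, and SAP section 1 says that the SAP is to be read together with it. The substitution sentence could even mean that such a patient has MUGA throughout, although its position after the triggered ECHO makes a within-patient switch the more natural reading. This should keep switches few. It does not say how to analyse those that occur.

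**A route for deviations exists.** SAP 4.3.7 has all protocol deviations reviewed, and their handling documented, before database lock. That stands, so it would be wrong to say that the SAP has no mechanism. What is missing is a pre-specified LVEF rule. The same section says "None of the deviations should lead to subjects being excluded from any analysis populations described in the SAP, unless otherwise specified", which concerns populations and does not settle which scans enter a change score. A rule could also sit in the separate output specifications, which were not available.

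**The SAP as a whole covers the schedule.** A reader of 5.6.10.1 alone might conclude that the SAP omits MRI and scheduled scans. Tables 7 and 8 carry the full MUGA/MRI/ECHO row, so the gap is confined to that paragraph.

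**No planned analysis was altered.** SAP sections 3 and 9 record no changes to protocol-planned analyses. Protocol 9.4.3 plans no LVEF analysis, so those entries are not shown to be wrong.

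**LVEF is descriptive.** It is not a listed endpoint in protocol Table 2. Cardiac risk is also followed by ECGs, troponin, BNP and QRS amplitude as an event of special interest. DLT and cardiac discontinuation rules rest on graded findings assessed by the investigator. All of this stands and limits the importance of the point.

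**Conclusion.** The point holds as a minor one. The SAP's substitution text conflicts with the protocol's one-modality rule, and no SAP rule keeps a switched pair out of the LVEF change summary. The consequence is a possible method artefact, in either direction, in a descriptive table.

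Its size cannot be fixed from the documents: it needs the between-modality offset, the number of switches and the group sizes, all of which were assumed above. With no switches the effect is zero.

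Two stronger readings are tempting and are not supported:

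- **That a switch could push a patient across the 50% LVEF limit.** From an assumed 55%, an offset of 3 gives 52% and of 4 gives 51%; only 5 or more reaches 50%. In any case that limit is a screening criterion in protocol 5.1, met before any on-treatment switch, and the documents attach no on-treatment rule to it.
- **That dose escalation or DLT calls could go wrong.** No such decision is shown to use the LVEF change table.

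**What to change.** 1. **SAP 5.6.10.1.** Reconcile it with protocol 8.2.5.1 and SAP Table 8: name all three modalities, include the scheduled scans, make the substitution sentence agree with the within-patient rule, and resolve the end-of-treatment versus 30-day timing of the repeat scan. Which timing applies is for the study team to settle.
2. **SAP 5.6.10.2.** Base the main summary of LVEF change and percentage change on scans of the same modality as the patient's baseline scan.
3. **Keep the other scans in view.** Retain off-modality scans in the absolute-value summary and in a listing that shows and flags modality, and state how many patients and scans were affected. Dropping them altogether would be worse, because the substitution follows an abnormal ECG and the patients lost would be those with a suspected cardiac effect.

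The cost is some SAP wording and one programming condition, provided that modality is held with each LVEF value. The downside is that a few off-modality scans leave the main change summary.
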